10. EVALUATION OF IMMUNOGENICITY

The immunogenicity analysis will be performed on the safety population.

Immunogenicity data (overall ADA results and titers, and neutralizing ADA results and isotype of ADA where applicable, and time to seroconversion) will be listed by analysis tier; specifically:

Tier 1: Screening assay ADA results (positive/negative)

Tiers 2 and 3 Humira and M923 will be used to confirm the positive status of samples scored potentially positive by the screening assay:

Tier 2: Confirmatory EU Humira assay (positive/negative); if negative this will be followed by

Tier 3: Confirmatory M923 assay (positive/negative)

Positive confirmatory assay results will be summarized by Tier (2 and 3) and overall positive (in either tier).

The number and percent of subjects testing positive for ADA or neutralizing antibodies before the dose of M923 or EU RPP and at scheduled postdose assessments will be presented by treatment arm. The time to seroconversion will be summarized by treatment arm using mean, median, standard deviation and range where appropriate.

The number and percentage of subjects who had at least one ADA-positive result will be provided by treatment arm. Similar analysis may be performed for subjects with predose

ADA-negative results and with at least one, two or three postdose ADA-positive result as appropriate. Similar analysis may also be performed for subjects with ADA titers within certain ranges (to be determined).

The immunogenicity following the transition from EU RPP to M923 as compared with continuous use of EU RPP will be evaluated with the number and percentage of subjects who had at least one ADA-positive by treatment arm and by treatment period (similar to those defined in the study protocol section 13.4.4.2). Analyses of immunogenicity will be performed both for ADA and nADA for AEs before and after ADA positive at any time. Overall AEs by ADA positive at any time or negative at all visits and Hypersensitivity reactions, including those identified via MedDRA SMQ vs ADA positive at any time. This will then be repeated for injection site reactions.

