10.3.2 Treatment Visits

During the double-blind treatment period (Weeks 1 to 48), subjects will return to study site according to the schedule presented in [Table 1](#).

Subjects will self-administer 40 mg of M923 or EU RPP every 2 weeks (Q2W) starting at Week 1 of the study.

Prior to administration of IP, the following assessments will be done at all visits unless otherwise indicated:

- Patient-reported questionnaires: DLQI and EQ-5D-5L (to be completed prior to any other assessments being done [Weeks 16, 25, and 37])
- Review of concomitant medications/non-drug therapies
- AE monitoring
- sPGA, PASI, BSA evaluation

- Brief physical examination (Weeks 4, 8, 17, 19, 25, 27, 37, and 39; complete physical examination at Week 16)
- Vital signs (body temperature, pulse rate, blood pressure, respiratory rate, and measure body weight)
- 12-lead ECG (Weeks 16, 25, and 37)
- PK and immunogenicity (Weeks 8, 16, 17, 21, 25, 29, 37, and 41)
- Clinical laboratory assessments (hematology and serum chemistry; all visits, except Weeks 12, 27, 33, 39, and 45)
- Urinalysis (Weeks 4, 8, 16, 17, 19, 21, 25, and 37)
- Urine pregnancy test (female subjects of childbearing potential only; all visits, except Weeks 1, 19, 27, 39 and 45)
- Study drug dispensing
- Study drug injection in clinic by subject or caregiver (as directed by study site staff)(Weeks 1, 17, 19, 21, 25, 27, 37, and 39)
 - Post-injection monitoring for 2 hours post-injection (clinic only; Weeks 1, 17, 25, and 37)
 - Post-injection observation for 30 minutes post-injection (clinic only; Weeks 19, 21, 27, and 39)
- Study drug injection at home, but after assessments completed at clinic visit (Weeks 29, 33, 41, and 45)
- Study drug injection at home in-between clinic visits (Weeks 3, 5, 7, 9, 11, 13, 15, 23, 31, 35, 43, and 47)
- Injection site evaluation either by clinical staff (at clinic visits) or by the subject or caregiver (administration at home) per [Section 12.10](#)

At Week 16, subjects in Arm B will be randomly assigned again to a new treatment group:

- Arm B1: Continues EU RPP from Weeks 17 through 48 (last dose at Week 47; n = up to 129 subjects)
- Arm B2: Transition to M923 at Week 17; then to EU RPP at Week 25; and to M923 at Week 37 (last dose at Week 47; n = up to 129 subjects)

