2.1 Study Population

The study population will include 516 randomized subjects (258 subjects randomized to the M923 group and 258 subjects randomized to the EU RPP group) with moderate to severe chronic plaque-type psoriasis. Subjects will be eligible for the study provided that they satisfy all of the eligibility criteria listed in the study protocol.

The 2 treatment arms are:

- Arm A: M923 from Weeks 0 to 48 (last dose at Week 47)
- Arm B: EU RPP from Weeks 0 to 16 (last dose at Week 15); then randomized again at Week 16 into Arms B1 and B2:
 - Arm B1: Continues EU RPP from Weeks 17 through 48 (last dose at Week 47; n = up to 129 subjects)
 - Arm B2: Transition to M923 at Week 17; then to EU RPP at Week 25; and to M923 at Week 37 (last dose at Week 47; n = up to 129 subjects)

At Week 25, subjects not achieving at least a PASI50 response will be discontinued from the study. The last dose of study drug will be administered at Week 47. Subjects will be followed for safety until Week 52.

The overall study design can be seen in the study protocol ([Figure 1](#))

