- For subjects who do not have any post-baseline data and did not discontinue the study treatment due to AE(s) or death prior to the Week 16 visit, missing values will not be imputed and subjects will be excluded from the analysis.

Mixed Models for Repeated Measures (MMRM): As a supportive analysis, continuous PASI scores will be imputed based on mixed-effects model for repeated measures (MMRM). Categorical endpoints will be derived from the imputed continuous measure. The MMRM model will use PASI data from the Week 0 to Week 16 visits and will

include covariates for baseline PASI score (continuous), treatment group (A, B), visit (Week 1, 4, 8, 12 and 16), region (North America, Western Europe, or Eastern Europe/Asia), and the treatment-by-visit interaction. An unstructured variance-covariance matrix will be estimated. If the procedure fails to converge a heterogenous Toeplitz structure will be used for the variance-covariance matrix. The Kenward-Roger method will be used for estimating degrees of freedom.

Observed Case: As a supportive analysis for PASI scores, the observed data, with no imputation for missing data, will be summarized with descriptive statistics.

Adverse Events

At database lock and before the unblinding occurs, all AEs will be checked for missing causality assessment and/or severity grades. Any missing cases, will be reviewed by pharmacovigilance monitor or designee and appropriate data handling decisions will be provided on case by case.

Other Outcome Measures

Unless otherwise specified, for all other outcome measures, descriptive statistics will be presented in tables, with no action to handle missing data (observed case). Subjects who withdraw prior to the last planned observation in the study period will be included in the analyses up to the time of withdrawal.

Extra measurements (such as unscheduled or repeat assessments) will not be included in the descriptive statistics, but will be included in subject listings.

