9. EVALUATION OF PHARMACOKINETICS

Secondary PK outcome measures will be analyzed using the PK Analysis set.

For the interim analysis, this will include adalimumab concentration and immunogenicity data through Visit 11, Week 25 and will reflect 5 post-dose assessments on Weeks 8, 16, 17, 21 and 25.

Adalimumab serum levels will be summarized by treatment arm at each scheduled collection. In addition to the usual descriptive statistics, the geometric mean, corresponding 95% confidence interval (CI), and geometric coefficient of variation (CV) will also be presented. Concentrations that are below the limit of quantitation (BLQ) will be replaced with the lower limit of quantitation (LLOQ) for the computation of descriptive statistics. Missing concentrations will be treated as missing. Individual and geometric mean (95% CI) adalimumab concentrations will be graphically presented by treatment (A vs B through Week 16 and versus B1 and B2 following re-randomization).

To evaluate whether anti-adalimumab antibody formation will affect exposure, the summaries will be further stratified by ADA formation (subjects who did not form antibodies, subjects who formed ADAs, subjects who did not form neutralizing ADAs, versus subjects who formed neutralizing ADAs), as appropriate.

Figures will be also be generated to display arithmetic mean adalimumab concentrations versus study week grouped by treatment. Scatterplots and boxplots will also present

adalimumab concentrations stratified by ADA status and to explore the relationship between trough concentrations and ADA titres.

The within-subject variability (geometric CV) in trough concentrations (2 weeks postdose samples) over time (Week 17 to Week 41) will be determined for each subject, which will then be listed, summarized, and compared between treatment arms (EU RPP/EU RPP versus EU RPP/M923) using an analysis of variance model with treatment as a fixed effect. For the subgroup in the EU RPP treatment which is randomized to transition to M923 and back, the troughs

- collected in Weeks 21 and 25 fall into the first transition to M923,
- collected in Weeks 29 and 37 fall into the transition back to EU RPP,
- collected in Week 41 falls into the second transition to M923.

The transition from EU RPP to M923 as compared with continuous use of EU RPP with regard to PK will be evaluated using the descriptive statistics at each schedule time point and statistical comparison of within-subject variability.

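### Time to seroconversion is summarised without a censoring rule, so it describes converters only and is a poor comparison between arms

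*SAP*

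**What the plan says.** SAP section 10 states: "The time to seroconversion will be summarized by treatment arm using mean, median, standard deviation and range where appropriate". Protocol 13.4.4.3 plans the same statistics. The analysis set is broad: "The immunogenicity analysis will be performed on the safety population". It therefore includes subjects who never become ADA-positive.

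Neither document gives this variable a time origin, a censoring date, a Kaplan-Meier or cumulative-incidence estimate, or a rule for subjects without the event. SAP 5.2 handles outcomes other than the PASI and sPGA measures and adverse events as observed cases, without imputation. On withdrawals it says: "Subjects who withdraw prior to the last planned observation in the study period will be included in the analyses up to the time of withdrawal". That does not settle what time, if any, a withdrawn negative subject contributes.

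Post-dose ADA samples are scheduled at Weeks 8, 16, 17, 21, 25, 29, 37 and 41 (Protocol 10.3.2), at Week 48 (10.3.3) and at Week 52 (10.3.4). For the interim analysis, SAP section 9 says the data "will reflect 5 post-dose assessments on Weeks 8, 16, 17, 21 and 25".

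SAP section 10 also plans proportions: "The number and percentage of subjects who had at least one ADA-positive result will be provided by treatment arm". It adds the number and percentage positive before dosing and at each scheduled post-dose assessment by arm, and ever-positive counts by treatment period for the transition comparison.

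**The concern.** A mean, SD or range needs a time for every subject it covers. Subjects who stay negative have none, and observed-case handling supplies none. The only computable version is therefore restricted to converters, which conditions on the outcome being described.

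That removes most of the information that separates arms. If one product converts more subjects but the timing among converters is similar, the planned statistic hardly moves. Early withdrawal also cuts off late conversions and lowers the mean with no change in immunogenicity.

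Immunogenicity against the EU reference product, and after transition from it, belongs to the secondary objectives. A by-arm time summary invites comparison between arms, and similar values could be taken as reassurance they do not provide.

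**Working it through.** The documents state no figure for time to seroconversion and no expected seroconversion rate, so there is nothing to reproduce. The check asks how the planned statistic behaves over a range of assumed rates.

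**Inputs from the documents.** The post-dose samples are v = 8, 16, 17, 21, 25, 29, 37, 41, 48 and 52 weeks. The planned arm size comes from SAP 2.1: "258 subjects randomized to the M923 group and 258 subjects randomized to the EU RPP group".

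**Assumptions.** Onset has a constant hazard. A proportion c, from 20% to 90%, has converted by Week 48. Onset is detected at the next scheduled sample, and there is no dropout in the main table.

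**Formulas.**
- Hazard: λ = −ln(1 − c)/48.
- Cumulative conversion at visit v: F(v) = 1 − exp(−λv).
- Share detected at visit j: p_j = F(v_j) − F(v_{j−1}).
- Converter-only mean: m = Σ p_j v_j / F(52).
- Restricted mean seroconversion-free time to Week 52, over all subjects: R = F(52)·m + (1 − F(52))·52.

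**Worked case, c = 20%.** λ = −ln(0.8)/48 = 0.00465. F at the ten visits is 0.0365, 0.0717, 0.0760, 0.0930, 0.1097, 0.1261, 0.1580, 0.1735, 0.2000 and 0.2147. Σ p_j v_j = 6.03, so m = 6.03/0.2147 = 28.1 weeks. R = 6.03 + 0.7853 × 52 = 46.9 weeks.

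| Converted by Week 48 | F(52) | Converter-only mean (SD), weeks | Converter-only median | Restricted mean, all subjects, weeks |
|---|---|---|---|---|
| 20% | 0.215 | 28.1 (14.55) | Week 25 | 46.9 |
| 40% | 0.425 | 26.8 (14.43) | Week 25 | 41.3 |
| 60% | 0.629 | 25.0 (14.15) | Week 21 | 35.0 |
| 80% | 0.825 | 22.2 (13.38) | Week 16 | 27.4 |
| 90% | 0.917 | 19.7 (12.38) | Week 16 | 22.4 |

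**Reading the table.** From 20% to 40% the planned mean moves 28.1 − 26.8 = 1.3 weeks, and the restricted mean moves 46.9 − 41.3 = 5.6. From 20% to 60% the moves are about 3 and 12 weeks.

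**Precision, 20% versus 40%, 258 per arm.** Converters number 258 × 0.2147 = 55.4 and 258 × 0.425 = 109.7. The standard error of the difference in means is √(14.55²/55.4 + 14.43²/109.7) = 2.4 weeks, nearly twice the difference itself. It would be larger with Arms B1 and B2, planned at up to 129 each.

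**Interim schedule.** With samples to Week 25 and 20%, 40% and 60% converted by Week 25, the means are 15.3, 14.9 and 14.2 weeks. The median is Week 16 in all three.

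**Other onset shapes.** With a Weibull shape of 0.5 and rates set at Week 52, the means at 20%, 40% and 60% are 20.4, 19.4 and 17.9 weeks. If all converters share one onset distribution, the difference is exactly zero at any pair of rates.

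**Dropout.** Take 40% true conversion by Week 48, samples to Week 48, and random dropout rising from 0% to an assumed 30% by Week 48. The converter-only mean falls from 25.2 to 23.9 weeks. The crude ever-positive proportion falls from 40.0% to 33.3%.

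**The case against.** The strongest reply is that SAP section 10 already reports what matters. ADA-positive numbers and percentages are tabulated by arm at every visit, for at least one positive result, and by treatment period. Were 20% versus 40% tested at two-sided 5% with 258 per arm, power would be about 99.9%. Time to seroconversion is absent from the outcome measures in SAP 3.3 and Protocol 8.4.2.3, which list proportion, titer and neutralizing ADA. SAP section 5 confines formal testing to the primary outcome. All of this stands. A reader might infer that the plan would hide a difference in immunogenicity between the products; the separate tables contradict that.

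A reader might also infer that the converter-only mean is insensitive at any rates. It is not: under constant hazard it falls about 6 weeks from 20% to 80% and about 8 weeks from 20% to 90%.

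Nor should the planned figures be set against underlying median onset times. At 20% the constant-hazard median is ln 2/λ = 149 weeks, far beyond the last sample at Week 52. No analysis of these data could estimate it, and Kaplan-Meier would show the median as not reached at both 20% and 40%.

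Ordinary Kaplan-Meier does not remove dependence on the visit schedule either, since its steps fall on the same visits. Only an interval-censored estimate addresses that.

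Finally, the SAP does not say that only converters are included. That follows from its silence, and onset timing among converters is a legitimate description if labelled as such. The phrase allowing the statistics where appropriate supplies no label, denominator or rule.

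**Conclusion.** The point holds as a defect in one descriptive statistic. With no censoring rule, the summary conditions on conversion, leaves out subjects who stay negative or leave early before converting, and compares arms poorly. For assumed rates of 20% to 60% the planned mean shifts by about 3 weeks against an SD of about 14, where the all-subject restricted mean shifts by about 12. The contrast is less stark at 80% to 90%.

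The rates, onset shapes and dropout are all assumptions. The missing rule is not: it can be read in both documents. The consequence is a possibly misleading secondary table. It does not threaten the primary conclusion or the ability to see different seroconversion rates. A censored estimate would add something the ever-positive proportion lacks, namely allowance for unequal follow-up, provided censoring is non-informative.

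**What to change.** Change SAP section 10 and Protocol 13.4.4.3 together.

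- Define the event (first confirmed ADA-positive sample), the time origin, and censoring of non-converters at their last ADA sample.
- Report cumulative seroconversion by arm among subjects ADA-negative at baseline. Use an interval-censored estimate, or Kaplan-Meier with steps stated to fall at the sampling visits.
- Give estimates with 95% confidence intervals at Weeks 16, 25 and 48. Compare A with B to Week 16, then B1 with B2 among subjects still ADA-negative at re-randomisation.
- State that censoring is assumed non-informative. Note the planned discontinuation at Week 25 of subjects without a PASI50 response as a place where that assumption needs comment.
- If the mean, median, SD and range are kept, label them as converters only and give n for each arm.

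No new data are needed. The cost is revised wording and one extra standard analysis.

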8.4.2.3 Pharmacokinetics and Immunogenicity

1. Exposure to M923 and EU RPP assessed as serum levels collected periodically throughout the treatment period
2. Immunogenicity of M923 and EU RPP assessed as proportion experiencing seroconversion, titer of anti-drug antibody (ADA) levels over time, and neutralizing ADA

3. Immunogenicity, as evidenced by the presence of ADAs, following the transition from EU RPP to M923 compared with continuous use of EU RPP assessed as proportion of subjects experiencing seroconversion; titer of ADA levels over time; and neutralizing ADA over time

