The immunogenicity following the transition from EU RPP to M923 as compared with continuous use of EU RPP will be evaluated with the number and percentage of subjects who had at least once ADA-positive by treatment arm and by treatment period (as defined in the [Section 13.4.4.2](#)).

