3.3 Pharmacokinetic and Immunogenicity Outcome Measures

1. Exposure to M923 and EU RPP assessed as serum levels collected periodically throughout the treatment period.
2. Immunogenicity of M923 and EU RPP assessed as proportion experiencing seroconversion, titer of anti-drug antibody (ADA) levels over time, and neutralizing ADA over time.
3. Immunogenicity, as evidenced by the presence of ADAs following the transition from EU RPP to M923 compared with continuous use of EU RPP assessed as proportion of subjects experiencing seroconversion; titer of ADA levels over time; and neutralizing ADA over time through Week 25.

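### The transition outcome is defined as seroconversion, but the planned analysis counts every ADA-positive subject in a period, which dilutes the B2 versus B1 contrast

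*SAP*

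**What the plan says.** **Outcome.** SAP 3.3, item 3, sets the immunogenicity outcome for the switch as "compared with continuous use of EU RPP assessed as proportion of subjects experiencing seroconversion", together with ADA titre and neutralizing ADA. Protocol 8.4.2.3, item 3, uses the same measure: "assessed as proportion of subjects experiencing seroconversion".

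**Analysis.** SAP 10 states that immunogenicity after the transition "will be evaluated with the number and percentage of subjects who had at least one ADA-positive by treatment arm and by treatment period". Protocol 13.4.4.3 has the same count: "subjects who had at least once ADA-positive by treatment arm and by treatment period". Neither sets a condition on a subject's ADA status before the switch.

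**Related analyses in SAP 10.** One analysis starts from negative subjects: those with predose "ADA-negative results and with at least one, two or three postdose ADA-positive result as appropriate". It is worded as something that may be done, and it is not tied to status at Week 16 or 17. Separately, "The time to seroconversion will be summarized by treatment arm using mean, median, standard deviation and range where appropriate", so that summary is by arm only and is not timed from the switch.

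**Periods.** SAP 10 points to periods similar to those in Protocol 13.4.4.2. There Period 1 ends with Week 16 included, Period 2 runs from Week 16 to Week 25, and Period 4 runs from Week 37 to Week 48.

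**Week 25.** The last element of SAP 3.3, item 3, reads "neutralizing ADA over time through Week 25". Protocol 8.4.2.3 has no such limit.

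**The concern.** Secondary objective 2 asks whether moving from EU RPP to M923 is acceptable for safety and immunogenicity, compared with staying on EU RPP. The immunogenic effect of a switch shows mainly as new antibody in subjects who had none, and as rising titre in those who already had some.

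Arm B subjects have had EU RPP since Week 0 before the first switch dose at Week 17. Anyone who became positive in that time and stays positive is an event in every later period, in B1 and B2 alike, whatever the switch does. These subjects add equal counts to both arms and shrink the visible difference. A small difference in the planned table could then be read as reassurance about new seroconversion, which the table does not measure.

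**Working it through.** The documents give no ADA rate, power or sample size for this comparison, so there is no planned figure to reproduce.

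**1. Which samples fall after the switch.** ADA is sampled at Weeks 8, 16, 17, 21, 25, 29, 37 and 41 (Protocol 10.3.2), with further samples at baseline and Weeks 48 and 52. Samples are drawn before any dose at the visit (schedule footnote j). The first switch dose is at Week 17, so the Week 16 and Week 17 samples are both pre-switch. Week 16 sits on the boundary of Periods 1 and 2 and is named in both. Week 17 lies wholly in Period 2. The two-period split in SAP 5.4, which starts its second period after Week 16, does not change this. A subject positive only on the Week 17 pre-dose sample is therefore a Period 2 event before receiving any M923.

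**2. What the planned count estimates.** Let q be the share positive before the switch, r the share of those who stay positive, and c the new-conversion rate among negatives.

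- Planned proportion: P = q·r + (1 − q)·c
- Planned difference, with r equal in both arms: (1 − q)·(c_B2 − c_B1)
- Difference among pre-switch negatives: c_B2 − c_B1

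**3. Inputs.** From the documents: 258/2 = 129 per re-randomised arm. Assumed: c_B1 = 10%, c_B2 = 25%, r = 100%, and q from 5% to 60%. With SE = √[(p1(1−p1) + p2(1−p2))/n], the 95% half-width is 1.96·SE and detectability is Φ(d/SE − 1.96). For negatives, n = 129(1 − q). Detectability is only a yardstick for precision.

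**4. Example, q = 20%.**

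- Planned: p1 = 0.20 + 0.80 × 0.10 = 0.28; p2 = 0.20 + 0.80 × 0.25 = 0.40; d = 0.12; SE = √[(0.2016 + 0.2400)/129] = 0.0585; Φ(2.05 − 1.96) ≈ 54%.
- Negatives only: n = 103.2; d = 0.15; SE = √[(0.0900 + 0.1875)/103.2] = 0.0519; Φ(2.89 − 1.96) ≈ 82%.

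**5. Results (points ± 95% half-width).**

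| Positive before switch | Planned count | Detectability | New conversion among negatives | Detectability |
|---|---|---|---|---|
| 5% | 14.25 ± 9.9 | 81% | 15 ± 9.3 | 88% |
| 20% | 12 ± 11.5 | 54% | 15 ± 10.2 | 82% |
| 40% | 9 ± 12.2 | 31% | 15 ± 11.7 | 71% |
| 60% | 6 ± 11.5 | 18% | 15 ± 14.4 | 53% |

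At 40% and 60%, an interval centred on the true planned difference includes zero, while the one for new conversion does not. At 60% the planned interval is the narrower of the two in absolute terms, but its target has shrunk by more.

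**6. Sensitivity.** These figures use a pooled-variance calculation, which differs from the table by a point or two, at q = 20%, 40% and 60%.

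- 10% versus 20% new conversion: 28%, 16% and 10% (planned) against 52%, 41% and 30% (negatives).
- 20% versus 40%: 74%, 50% and 30% against 89%, 78% and 61%.
- Persistence of 90% leaves the planned difference unchanged and moves its detectability by at most about 3 percentage points.

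**7. Noise from carried-over positives.** The SD of the chance difference in prior positivity between B1 and B2 is √[2q(1 − q)/129]: 5.0 points at 20% and 6.1 points at 40% or 60%.

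**The case against.** **It is not bias.** A reader might infer that the plan is biased toward finding no effect of switching, or chosen for that reason. The documents support neither. B1 and B2 are re-randomised, so prior positives balance in expectation. The any-positive difference is a valid estimate of the difference in period prevalence across everyone re-randomised. It answers a different question from the one in SAP 3.3. This objection stands.

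**No test is planned.** SAP 5 limits formal testing to the primary outcome and gives differences with 90% and 95% intervals elsewhere. The detectability figures therefore describe no planned decision. This stands, although the diluted contrast would still be displayed and interpreted.

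**The size is assumed.** At 5% prior positivity the contrast falls only from 15 to 14.25 points. The final analysis also covers 572 subjects, so 572/4 = 143 per re-randomised arm before dropout, which gives about 58% against 86% at 20% prior positivity. This stands.

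**Much of the information is already there.** SAP 10 plans positivity at each scheduled assessment, and listings of ADA results, titres and time to seroconversion. New conversions could be derived from those. True, but no required table conditions on pre-switch status, and deriving one later would be post hoc.

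**The Week 25 phrase.** A reader might infer that SAP 3.3 drops the second switch to M923 at Week 37. The list is separated by semicolons, and the phrase most naturally limits only neutralizing ADA. SAP 10 refers to periods running to Week 48, and SAP 5.1 says the SAP serves both the interim and final reports. The wording may be left over from the interim cut. It needs reconciling, but it does not show that the Week 37 switch goes unanalysed.

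**Conclusion.** The mismatch is clear on the text. Both documents define the transition outcome as seroconversion, both evaluate it as period prevalence, and no mandatory analysis supplies new seroconversion after the switch. The period boundaries also place a pre-switch sample after the switch.

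The consequence is dilution by the factor (1 − prior positivity), plus noise from carried-over positives. The factor assumes equal persistence of prior positives in B1 and B2, and its practical size depends on a prior-positive rate that the documents do not give. The loss is minor near 5% and substantial from about 20% upward under the illustrated conversion rates. This affects how a descriptive secondary result can be read and does not touch the primary equivalence analysis. It should be changed because the correction is cheap and the samples are already in the schedule.

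**What to change.** In SAP 10:

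1. Assign every ADA sample up to and including the Week 17 pre-dose sample to the pre-switch period.
2. Make mandatory a B2 versus B1 table of new confirmed ADA-positive subjects after the Week 17 dose, and separately new neutralizing-ADA positives. The risk set is subjects negative on all samples up to and including Week 17 pre-dose. Give the difference with 90% and 95% intervals, and show it by period. Both arms have received only EU RPP up to that sample, so this restriction keeps the randomised comparison.
3. Add a descriptive table for the second M923 switch, among subjects still negative at the Week 37 pre-dose sample. Otherwise conversions after the Week 17, 25 and 37 changes are pooled. It stays descriptive because that risk set depends on what happened after re-randomisation.
4. Report titre rise separately in subjects positive before the switch.
5. Keep the any-positive table as supportive.

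In SAP 3.3, item 3, reconcile the Week 25 limit with Protocol 8.4.2.3 and the SAP 10 periods, by deleting it or marking it as the interim cut only.

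The cost is SAP wording and one or two more tables, with no new data. The downside is a smaller denominator: for example 129 × 0.6 ≈ 77 per arm at 40% prior positivity.
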